8. STUDY ASSESSMENTS AND PROCEDURES

Study procedures and their timing are summarized in the SoA ([Table 1](#)). Protocol waivers or exemptions are not allowed.

Immediate safety concerns should be discussed with the Sponsor immediately upon occurrence or awareness to determine if the participant should continue or discontinue study intervention.

Adherence to the study design requirements, including those specified in the SoA, is essential and required for study conduct.

All Screening evaluations must be completed and reviewed to confirm that potential participants meet all eligibility criteria. The Investigator will maintain a Screening log to record details of all participants screened and to confirm eligibility or record reasons for Screening failure, as applicable.

Procedures conducted as part of the participant's routine clinical management (eg, blood count) and obtained before signing of the ICF may be used for Screening or baseline purposes provided the procedures met the protocol-specified criteria and were performed within the timeframe defined in the SoA.

The maximum amount of blood collected from each participant over the duration of the study, including any extra assessments that may be required, will not exceed approximately 300 mL.

Repeat or unscheduled samples may be taken for safety reasons or for technical issues with the samples.

Participant Identification Card

On Day 1 of Cycle 1, all participants will be given a participant identification card identifying them as participants in a research study. The card will contain study site contact information (including direct telephone numbers) to be used in the event of an emergency. The Investigator or qualified designee will provide the participant with a participant identification card immediately after the participant provides written informed consent.

Medical History

A medical history will be obtained by the Investigator or qualified designee. The medical history will collect all medical and surgical conditions that the Investigator considers to be clinically significant and relevant. Details regarding the disease for which the participant has enrolled in this study will be recorded separately and not listed as medical history.

Calibration of Equipment

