4.9.3 Clinical Laboratory Evaluation

Chemical laboratory assessments include hematology, clinical chemistry, routine urinalysis, and pregnancy testing. The laboratory tests required by the protocol are detailed in Appendix 10.2 of the protocol.

All laboratory assessments will use local laboratories with results reported on the CRF. As such, laboratory assessments will be summarized by the visit in which the assessment was conducted.

For by-visit summaries, visit windowing will be implemented as specified in Section 4.10.1.3. For across visit summaries (e.g., worst post-baseline value), scheduled, unscheduled and repeat assessments will be considered.

All laboratory tests with values considered clinically significantly abnormal during participation in the study or within 30 days after the last dose of study intervention should be repeated until the values return to normal or baseline or are no longer considered clinically significant by the investigator or medical monitor. When there are repeat laboratory tests conducted on samples collected during the same visit, the last non-missing assessment will be summarized.

Laboratory values for hematology and clinical chemistry will be summarized as raw, change from baseline, and maximum change from baseline (for the participant). Descriptive statistics (for non-categorical data) will be presented by line of therapy for both raw values (n, mean, standard deviation, median, minimum, maximum) and changes from baseline.

A summary of the incidence of abnormal, high, or low values will be created by line of therapy and visit. Shift tables will be created for hematology and clinical chemistry parameters for which normal ranges exist. Shift tables for CTCAE grade shifts from baseline to worst post-baseline will also be presented by line of therapy for hematology and clinical chemistry for low and high shifts separately.

For urinalysis, a summary of the incidence of abnormal, high, and low values will be created. Shift tables will not be created for urinalysis.

A separate summary of findings of potential drug induced liver injury (DILI) will be prepared. The number and proportion of participants meeting one or both of the following criteria at any post-treatment visit will be summarized:

- ALT or AST $3 \times$ ULN and total bilirubin $2 \times$ ULN ($> 35\%$ direct bilirubin) or
- ALT or AST $3 \times$ ULN and international normalized ratio (INR) > 1.5 .

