4.9.4 Vital Signs, Physical Findings, and Other Observations Related to Safety

Vital signs and ECGs will be summarized by line of therapy and timepoint.

The raw value and change from baseline will be summarized for vital sign parameters (weight, BMI, heart rate, respiratory rate, systolic blood pressure (SBP), diastolic blood pressure (DBP), and temperature). Additionally, post-baseline shift summaries will be presented for temperature, SBP, DBP, and weight. For subjects with multiple records at a visit, the latest record will be summarized.

The raw value and change from baseline will be summarized for abnormal/CS records for ECG parameters (RR, PR, QRS, QT, QT corrected by Bazett [QTcB], and QT corrected by Fridericia [QTcF]) by line of therapy and visit/timepoint (for raw values and change from baseline). Note that ECG parameters are only recorded for a subject if the overall assessment is abnormal/CS, so only abnormal/CS parameter responses are summarized. ECGs are also collected in triplicate, so average values will be presented where multiple assessments are abnormal, clinically significant at a timepoint. Additionally, post-baseline shift summaries will be presented for heart rate, PR, QRS, and QTcF.

A by participant, by-visit listing of vital signs also will be produced.

A separate summary of the number and proportion of participants experiencing clinically significant abnormal ECG findings will be summarized, including the specific ECG abnormality, by line of therapy and visit/timepoint.

QTcF will be graded per CTCAE v5.0 grading criteria. A summary of the number and proportion of participants with any QTcF abnormalities, with Grade 3 or higher abnormalities, and with clinically significant Grade 1 and 2 abnormalities will be produced by line of therapy and visit/timepoint as well as overall (any timepoint). Abnormal and clinically significant ECG findings will also be reported through the AEs.

Additional summaries of the QTcF data may be performed, such as the number and proportion of participants with:

- Absolute QTcF interval prolongation:
 - QTcF interval \geq 450 milliseconds
 - QTcF interval \geq 480 milliseconds
 - QTcF interval \geq 500 milliseconds
- Change from baseline in QTcF interval:
 - QTcF interval increases from baseline \geq 30 milliseconds
 - QTcF interval increases from baseline \geq 60 milliseconds

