4.10.1.3 Visit Windows

Analysis visit windows will be created based on the schedule of assessments in the protocol (Appendix 6.1) as shown below. Any visits outside the visit window will be considered “Unscheduled” and not summarized at a scheduled visit. If multiple records are mapped to the same visit, the one closest to the date of the scheduled assessment will be used. If there is an equal distance from the date of the scheduled assessment, the latest record will be used.

| Visit | Study Day Window |
|------------------|--|
| Screening | [-42, -1] |
| Cycle 1 Day 1 | 1 |
| Cycle 1 Day 15 | [13, 17] |
| Cycle 2 Day 1 | [27, 31] |
| ... | [expected day – 2 days, expected day + 2 days] |
| EOT/ED | [last dose day, last dose + 15 days] |
| Safety Follow-up | [last dose + 25 days, last dose + 35 days] |

For tumor evaluations, the following windows will be implemented:

| Visit | Study Day Window |
|---|--|
| Screening | [-42, -1] |
| Cycle 3 Day 1 | [50, 64] |
| Every 2 cycles (8 weeks) during first 12 months and every 3 cycles thereafter (12 weeks) until EOT/ED | [expected day – 7 days, expected day + 7 days] |
| EOT/ED | [last dose day, last dose + 15 days] |

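### By-visit laboratory summaries take the last repeat, although required repeats follow only clinically significant abnormal values, and the rule conflicts with the SAP's own visit-window rule

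*SAP*

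**What the plan says.** SAP 4.9.3 contains three statements that bear on each other.

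- Required repeats: a test judged abnormal to a clinically significant degree, on study or up to 30 days after the last dose, "should be repeated until the values return to normal or baseline or are no longer considered clinically significant by the investigator or medical monitor". Protocol 8.2.4 has the same requirement.
- Choice of record: "When there are repeat laboratory tests conducted on samples collected during the same visit, the last non-missing assessment will be summarized".
- Windows: "For by-visit summaries, visit windowing will be implemented as specified in Section 4.10.1.3".

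SAP 4.10.1.3 then gives its own rule: "If multiple records are mapped to the same visit, the one closest to the date of the scheduled assessment will be used". The latest record is used only when two are equally distant. On-treatment windows are the expected day ± 2 days, and anything outside is unscheduled and left out of the by-visit tables. The EOT/ED window runs from the day of last dose to 15 days after it.

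The tables concerned are the by-visit summaries of values and changes from baseline, and this one: "A summary of the incidence of abnormal, high, or low values will be created by line of therapy and visit". Change from baseline in laboratory parameters is a secondary safety endpoint (Protocol Section 3; SAP 3.2).

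For vital signs, SAP 4.9.4 says: "For subjects with multiple records at a visit, the latest record will be summarized".

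**The concern.** A by-visit table should show each participant's value at the visit, chosen without regard to what that value was. Here the choice depends on the result. A clinically significant abnormal first value must be repeated and can be superseded by the repeat. A normal first value triggers no required repeat and normally stands. For required repeats the selection therefore works in one direction.

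At stake are the by-visit means, the changes from baseline and the per-visit incidence of abnormal values in a trial whose main purpose is to describe safety. In addition, two sentences in the SAP can send a programmer to different records for the same participant and visit.

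**Working it through.** The plan states no figure for laboratory repeats, so there is nothing to reproduce. The check has four steps.

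**1. Direction.** Take a participant whose first value at a visit is abnormal and clinically significant, with a required repeat in the same visit. If the last repeat is still out of range, the abnormal count is unchanged; if it is back in range, the count drops by one. No required repeat can add to the count. Means and changes move toward normal to the extent that the repeat has done so.

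**2. Which record each rule selects.** Let the first sample be on day *o* and a later repeat on day *k*, both relative to the expected day, with −2 ≤ *o* < *k* ≤ 2. There are 10 such pairs. The 4.9.3 rule always uses the repeat. The 4.10.1.3 rule uses it only if |*k*| ≤ |*o*|, since a tie goes to the latest.

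| First sample day | Repeat days for which 4.10.1.3 uses the repeat | Repeat days for which it keeps the first sample |
|---|---|---|
| −2 | −1, 0, +1, +2 | none |
| −1 | 0, +1 | +2 |
| 0 | none | +1, +2 |
| +1 | none | +2 |

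The repeat is used in 10 of 10 pairs under 4.9.3 and in 6 of 10 under 4.10.1.3, so the rules disagree in 4 of 10. These are counts of possible day pairs, not expected frequencies. Under 4.10.1.3 a first sample drawn on the expected day is always kept against a repeat on a later day. Two samples on the same day are tied, so both rules then select the repeat.

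**3. Where a repeat can reach the table.**

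- On treatment, a repeat outside ±2 days never displaces the visit value. Protocol Table 6 has the blood count for most Grade 3 haematologic toxicity repeated at the next scheduled visit or within 7 days, and weekly counts in the complicated cases. Many repeats will therefore miss the window.
- At EOT/ED the window covers days 0 to 15 after the last dose, which is 16 days, with no single scheduled date from which to measure distance. Lerociclib has stopped, and Protocol 6.5.1.1 expects neutrophils to recover when it is withheld. The last value in that window is the one most likely to be a recovered one.

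**4. Possible size, on assumptions.** Let *p* be the share with an abnormal first value, *c* the share of those judged clinically significant, *r* the share of those repeated within the same visit, and *v* the share of repeats back in range. Under the last-value rule:

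reported rate = *p*(1 − *c·r·v*), so loss = *p·c·r·v*.

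The documents give none of these four quantities. With *p* = 20% and 50 participants per line of therapy (SAP 4.12), the true count is 0.20 × 50 = 10.0.

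| Assumed *c*, *r*, *v* | Loss | Reported count of 50 |
|---|---|---|
| 0.25, 0.10, 0.5 | 0.20 × 0.0125 = 0.25 points | 9.9 |
| 0.5, 0.25, 0.5 | 0.20 × 0.0625 = 1.25 points | 9.4 |
| 0.5, 0.5, 1 | 0.20 × 0.25 = 5 points | 7.5 |

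The loss is proportional to *p*: across the three settings it is 0.13 to 2.5 points at *p* = 10% and 0.5 to 10 points at *p* = 40%. It is zero if no repeat falls in the visit or none is back in range.

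**The case against.** The best defence is that the effect is narrow and the safety record remains complete. Clinically significant values are recorded as adverse events, listings show all results with high and low flags, and the worst-post-baseline summaries, including the CTCAE shifts, take scheduled, unscheduled and repeat values. All of that stands. A reader might infer that the rule hides toxicity or touches the primary endpoint; the documents do not support that. By-visit and worst-value tables also differ by design, so a difference between them is not in itself an error.

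A reader might also infer that every triggering value is replaced by a normal one. It is not. The repeat must fall in the same visit, and repeating may stop at baseline or once the value is no longer clinically significant, so an out-of-range last value still counts as abnormal. Nor are repeats confined to bad values: Protocol Section 8 adds that "Repeat or unscheduled samples may be taken for safety reasons or for technical issues with the samples".

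It is tempting to size the effect by supposing that every neutrophil count below 1.0 × 10⁹/L is repeated within the visit. Table 6 does not require that timing. The planned by-visit table classifies values as abnormal, high or low, and SAP 4.9.3 flags results against the reference range, not a Grade 3 cut-off. Measurement error also makes the share of single readings below such a cut-off a poor stand-in for the true share.

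On the conflict, same visit could be read as same day, and then the two rules agree. That removes the contradiction but leaves the repeat selected, because the tie rule picks the latest record. If 4.10.1.3 governs instead, much of the on-treatment problem goes, but same-day repeats and the EOT/ED window remain.

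For vital signs the documents require no repeat of abnormal values, so the selection argument does not carry over to SAP 4.9.4. Only the mismatch with 4.10.1.3 does.

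**Conclusion.** The point holds in a limited form. For by-visit laboratory tables, SAP 4.9.3 states a record-selection rule that depends on the result, and for required repeats it can only lower the abnormal count. It also conflicts with the closest-date rule that the same section invokes. The size cannot be determined from the documents. It is probably small on treatment, given the ±2-day window and the repeat timing in Protocol Table 6, and larger where repeats are same-day or fall in the EOT/ED window. The range of 0.25 to 5 points at a 20% true rate rests wholly on assumed repeat and recovery shares and is not an estimate. The consequence is confined to by-visit summaries of a secondary safety endpoint. This is a minor correction, worth making because it is specific and cheap.

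**What to change.** State one rule, in the same terms, in SAP 4.9.3 and 4.10.1.3 for laboratory by-visit summaries:

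- Use the first valid scheduled sample in the visit window.
- Treat repeats as unscheduled for by-visit tables, and include them in the worst-post-baseline summaries.
- Let a repeat replace the first sample only when that sample is recorded as technically invalid.
- Say that this overrides the latest-record tie rule of 4.10.1.3 for laboratory repeats. Without this, same-day repeats would still be selected.
- Apply the rule explicitly to EOT/ED, where closeness to a scheduled date has no reference point.

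For vital signs in 4.9.4, only align the latest-record sentence with 4.10.1.3.

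The cost is SAP wording and a record-selection flag. It needs no new data and does not affect how participants are managed. The downside for the sponsor is that by-visit abnormality rates may look slightly less favourable.

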4.9.4 Vital Signs, Physical Findings, and Other Observations Related to Safety

Vital signs and ECGs will be summarized by line of therapy and timepoint.

The raw value and change from baseline will be summarized for vital sign parameters (weight, BMI, heart rate, respiratory rate, systolic blood pressure (SBP), diastolic blood pressure (DBP), and temperature). Additionally, post-baseline shift summaries will be presented for temperature, SBP, DBP, and weight. For subjects with multiple records at a visit, the latest record will be summarized.

The raw value and change from baseline will be summarized for abnormal/CS records for ECG parameters (RR, PR, QRS, QT, QT corrected by Bazett [QTcB], and QT corrected by Fridericia [QTcF]) by line of therapy and visit/timepoint (for raw values and change from baseline). Note that ECG parameters are only recorded for a subject if the overall assessment is abnormal/CS, so only abnormal/CS parameter responses are summarized. ECGs are also collected in triplicate, so average values will be presented where multiple assessments are abnormal, clinically significant at a timepoint. Additionally, post-baseline shift summaries will be presented for heart rate, PR, QRS, and QTcF.

A by participant, by-visit listing of vital signs also will be produced.

A separate summary of the number and proportion of participants experiencing clinically significant abnormal ECG findings will be summarized, including the specific ECG abnormality, by line of therapy and visit/timepoint.

QTcF will be graded per CTCAE v5.0 grading criteria. A summary of the number and proportion of participants with any QTcF abnormalities, with Grade 3 or higher abnormalities, and with clinically significant Grade 1 and 2 abnormalities will be produced by line of therapy and visit/timepoint as well as overall (any timepoint). Abnormal and clinically significant ECG findings will also be reported through the AEs.

Additional summaries of the QTcF data may be performed, such as the number and proportion of participants with:

- Absolute QTcF interval prolongation:
 - QTcF interval \geq 450 milliseconds
 - QTcF interval \geq 480 milliseconds
 - QTcF interval \geq 500 milliseconds
- Change from baseline in QTcF interval:
 - QTcF interval increases from baseline \geq 30 milliseconds
 - QTcF interval increases from baseline \geq 60 milliseconds

By-participant, by-timepoint listings of ECG parameters will be produced including raw values, change from baseline, normal ranges, abnormal flags, and clinical significance flags.

Clinically significant physical examinations will be reported as AEs as specified in the protocol.

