| PROs: EORTC-QLQ-C30 (Version 3), EQ-5D-5L, FACIT Item GP 5 | X ^b | On Day 1 of each cycle (before any other study procedures) until disease progression, death, withdrawal of consent, loss to follow-up, or participant/legally acceptable representative decision, and at EOT. | | | | | | | |
| PRO: EORTC-QLQ-BR23 | X ^b | On Day 1 of every other cycle (before any other study procedures) until disease progression, death, withdrawal of consent, loss to follow-up, or participant/legally acceptable representative decision, and at EOT. | | | | | | | |
| Collection Of Information on New Anticancer Therapies and Pregnancy Status ^k , as Applicable | | | | | | | X | X | X |
| Survival Follow-Up | | | | | | | | | X ^k |

- a. A physical examination is to be performed on Day 1 of every cycle. According to Investigator's judgment, this can be an abbreviated physical examination.
- b. To be performed between Day -7 and Day -1. For safety laboratory collections, the Screening labs do not need to be repeated at C1D1 if C1D1 and Screening are within 7 days of each other.
- c. Results of clinical laboratory tests (hematology, clinical chemistry, coagulation, fasting lipid panel, and urinalysis) must be available prior to the administration of lerociclib on Day 1 of each cycle and on Day 15 of Cycle 1. Clinical laboratory tests may be obtained up to 24 hours prior to the scheduled visit.

- d. For female study participants who are of childbearing potential (as defined in [Appendix 4](#)) only: Serum β -hCG pregnancy testing will be performed at Screening. Serum or urine β -hCG pregnancy testing will be performed at Day 1 of each cycle before the administration of lerociclib. At any timepoint during the study, pregnancy test(s) may be performed at the discretion of the Investigator.
- e. Participants will receive 12-lead ECGs (triplicate) at predose and at 2 hours and 6 hours (\pm 10 minutes) after their lerociclib dose on Day 1 and Day 15 of Cycle 1, and then on Day 1 of Cycles 2, 3, 4, and 5. Triplicate 12-lead ECGs shall be obtained within a 5-minute period and shall be performed prior to blood draws whenever applicable. The same make and model of ECG machine should be used within each participant. In addition to triplicate 12-lead ECGs, a single 12-lead ECG will be collected (prior to blood draws) at Screening and at the EOT/ED Visit. Other than at the EOT/ED Visit, ECGs will not be conducted beyond Cycle 5 unless clinically indicated.

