3. OBJECTIVES AND ENDPOINTS

Table 3: Study Objectives and Endpoints

| Objectives | Endpoints |
|---|--|
| Primary To characterize the safety and tolerability of lerociclib in combination with endocrine therapy in participants with 1L and 2L HR+/HER2- mBC | 
 Incidence of AEs and SAEs |
| Secondary To investigate the efficacy of lerociclib in combination with endocrine therapy in participants with 1L and 2L HR+/HER2- mBC by line of therapy | 
 Objective response rate, defined as the proportion of participants with a best overall response of CR or PR according to RECIST v1.1 as assessed by Investigator Clinical benefit rate, defined as the proportion of participants with a best overall response of CR, PR, or SD (for at least 8 weeks) according to RECIST v1.1 as assessed by Investigator Progression-free survival, defined as the time from first dose of lerociclib until the date of documented PD or death, according to RECIST v1.1 as assessed by Investigator Overall survival, defined as the time from the date of first dose of lerociclib to the date of death due to any cause Duration of response, defined as the time from the date of first documented response until the date of confirmed PD or death, according to RECIST v1.1 as assessed by Investigator Time to response, defined as the time from first dose of lerociclib until the first documented response (CR or PR) |
| To further characterize the safety and tolerability of lerociclib in combination with endocrine therapy in participants with 1L and 2L HR+/HER2- mBC | 
 Change from baseline in clinical laboratory parameters (hematology, clinical chemistry, coagulation, fasting lipid panel, and urinalysis) Change from baseline in vital signs and 12-lead ECG parameters |

Table 3: Study Objectives and Endpoints (Continued)

| Objectives | Endpoints |
|---|--|
| To assess change from baseline in global health status and QoL in participants with 1L and 2L HR+/HER2- mBC by line of therapy | 
 • Change from baseline in the Global Health Status/QoL Scale Score of the EORTC-QLQ-C30 • Change from baseline in the Global Health Status/QoL Scale Score of the EORTC-QLQ-BR23 • Change from baseline in the Global Health Status/QoL Scale Score of the EQ-5D-5L • Change from baseline in the Global Health Status/QoL Scale Score of the FACIT Item GP-5 |

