5.2. Exclusion Criteria

Prospective participants are excluded from the study if **any** of the following criteria apply:

Medical Conditions

1. Has symptomatic visceral disease or any disease burden that makes the participant ineligible for endocrine therapy, per the Investigator's best judgment.
2. Has peritoneal carcinomatosis.
3. Has inflammatory breast cancer at Screening.
4. Has CNS involvement, **unless** participant is at least 4 weeks from prior therapy completion to starting study treatment, has stable CNS tumor at the time of Screening, and is not receiving steroids and/or enzyme-inducing anti-epileptic medications for brain metastases.
5. Has any clinically significant, uncontrolled heart disease and/or cardiac repolarization abnormality.
6. Has a history of prolonged QT syndrome or Torsades de Pointes.

Prior/Concomitant Therapy

7. Has received prior treatment with chemotherapy (**except** neoadjuvant/adjuvant chemotherapy), or with any CDK4/6 inhibitor.
8. Has received prior treatment with fulvestrant.
9. Use of systemic estrogens (eg, hormonal contraception, HRT).
10. Is currently receiving any of the following substances and cannot be discontinued 14 days prior to starting lerociclib:
 - Known strong or moderate CYP3A inducers or strong inhibitors of CYP3A

- Substances that have a narrow therapeutic window and are predominantly metabolized through CYP3A4/5
11. Has evidence of active bacterial infection, fungal infection, or viral infection (including SARS-CoV-2 or uncontrolled HIV, as noted below) which would preclude safe enrollment in the judgment of the Investigator.
- **Notes:**
 - The study SARS-CoV-2 requirements are determined by institutional standards (and local/country regulations, as applicable).
 - At Investigator discretion, any participant who tests positive and/or is symptomatic for SARS-CoV-2 during Screening may either be excluded from the study or delay enrollment until active infection has been excluded per institutional standards.
 - During the study, any SARS-CoV-2 testing is to be performed as clinically indicated for the individual participant. The Investigator must document the results of all tests performed. Any confirmed infection is to be recorded as an AE or, in the event that clinical manifestation warrants such, recorded and handled as an SAE as detailed in [Appendix 3](#).

Diagnostic Assessments

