8.2.3. Electrocardiograms

All 12-lead ECGs will be obtained as outlined in the SoA ([Table 1](#)), using an ECG machine that automatically calculates the heart rate and measures P-R, QRS, QT, QTcB, and QTcF intervals. The same make and model ECG machine should be used within each participant. Participants should rest in a semi-supine/supine position for at least 5 minutes prior to each ECG assessment.

At each timepoint at which triplicate 12-lead ECG recordings are required per the SoA, 3 individual ECG tracings should be obtained as closely as possible in succession, but no more than 2 minutes apart.

The Investigator or qualified designee should review the ECGs for any abnormalities as compared with predose ECGs.

A central ECG vendor will be used to collect and hold the ECGs in the event that the Sponsor has any questions related to the results. The ECG safety data collected for the clinical study report will be based on Investigator assessment.

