9.3.3. Secondary Endpoint(s) Analysis

9.3.3.1. Other Safety Endpoints

Observed values and changes from baseline in vital signs, 12-lead ECG readings, and clinical laboratory parameters will be tabulated at each visit; by visit summaries will be based on scheduled, nominal visits.

Toxicities for clinical laboratory parameters will be characterized according to NCI CTCAE v5.0. Shifts in NCI CTCAE toxicity grades will be summarized. Vital signs and clinically significant findings on physical examination will be listed by participant.

Dose reductions/modifications, interruptions, compliance, and participant exposure will be summarized for each study therapy component, where appropriate.

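### The SAP limits ECG interval recording and summaries to ECGs judged abnormal and clinically significant, so the protocol's ECG change-from-baseline endpoint cannot be computed for most participants

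*SAP*

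**What the plan says.** The protocol (Section 3, Table 3) lists as a secondary safety endpoint: "Change from baseline in vital signs and 12-lead ECG parameters". SAP 3.2 repeats it. Protocol 9.3.3.1 gives the analysis: "Observed values and changes from baseline in vital signs, 12-lead ECG readings, and clinical laboratory parameters will be tabulated at each visit". Neither place limits this to abnormal tracings.

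The data are generated for everyone. The Schedule of Activities (footnote e) states: "Participants will receive 12-lead ECGs (triplicate) at predose and at 2 hours and 6 hours", on Days 1 and 15 of Cycle 1 and Day 1 of Cycles 2 to 5, with single ECGs at Screening and EOT/ED. Protocol 8.2.3 requires recording "using an ECG machine that automatically calculates the heart rate and measures P-R, QRS, QT, QTcB, and QTcF intervals".

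SAP 4.9.4 then narrows both capture and analysis:

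- Capture: "Note that ECG parameters are only recorded for a subject if the overall assessment is abnormal/CS, so only abnormal/CS parameter responses are summarized".
- Summary: "The raw value and change from baseline will be summarized for abnormal/CS records for ECG parameters".
- Triplicates: "average values will be presented where multiple assessments are abnormal, clinically significant at a timepoint".

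The same section plans shift summaries for heart rate, PR, QRS and QTcF. It also plans a CTCAE-graded QTcF table that counts abnormalities of any kind separately from clinically significant Grade 1 and 2 ones, and by-timepoint listings with separate abnormality and clinical-significance flags. QTcF threshold and increase categories are optional. SAP 4.13 says that the protocol's statistical methods are unchanged.

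**The concern.** The endpoint asks how ECG intervals move under lerociclib in the treated population. The SAP's rule keeps an interval only after someone has judged the ECG abnormal and clinically significant. That has three consequences.

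- A participant whose baseline ECG is unremarkable has no baseline number. If that participant later develops a clinically significant prolongation, the later value is kept but the change cannot be calculated. This is the participant for whom the change matters most.
- Drift within the range called normal or not clinically significant never enters the data.
- The remaining values are conditioned on a judgment that may itself depend on the interval, so their mean does not describe the study population.

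Characterising safety is the trial's primary objective, and participants undergo a dense triplicate schedule through Cycle 5. A table titled change from baseline in ECG parameters could be read as a population summary when it is not one.

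**Working it through.** The plan states no ECG figure to reproduce. The core of the check is logical; the simulation only illustrates size.

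**1. What is planned.** From footnote e: 6 visit days × 3 timepoints × 3 replicates + 2 single ECGs = 56 tracings per participant. For 100 participants, 56 × 100 = 5,600. This is a maximum, since it needs every participant to reach Cycle 5 and the EOT/ED visit.

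**2. When a change exists.** Change = later value − baseline value, where SAP 4.2.1 takes baseline as the last assessment before treatment. Under SAP 4.9.4 (CS = abnormal and clinically significant):

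| Baseline ECG | Later ECG | Change computable? |
|---|---|---|
| not CS | not CS | no, neither value recorded |
| not CS | CS | no, baseline missing |
| CS | not CS | no, later value missing |
| CS | CS | yes |

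No rule supplies the missing values. The SAP's stated convention, in its efficacy section (4.10.1.1), is to present data as observed.

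**3. How often the baseline is CS.** Inclusion criterion 7 requires baseline QTc below 470 msec. Exclusion criterion 5 reads: "Has any clinically significant, uncontrolled heart disease and/or cardiac repolarization abnormality". Criterion 6 excludes a history of prolonged QT syndrome or Torsades de Pointes. A CS baseline ECG should therefore be uncommon, though not impossible.

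**4. Internal consistency of SAP 4.9.4.** A count of QTcF abnormalities of any kind, shifts from a baseline category, and a significance flag separate from an abnormality flag all need values from ECGs that are not CS. Under the recording rule those values do not exist.

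**5. Illustration of size.** All distributional inputs are assumptions, not figures from the documents: baseline QTcF mean 420 msec; between-person SD 18, occasion SD 8, replicate SD 6; 17 later triplicate timepoints (6 × 3 − 1); a tracing called CS when its QTcF reaches a fixed cut; baseline triplicate mean below 470; 400 simulated trials of 100. Results per 100 participants, for true shifts of 0 / 10 / 20 msec:

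| CS cut (msec) | Baseline recorded | Change computable | Increase ≥30 msec, true | Increase ≥30 msec, detectable |
|---|---|---|---|---|
| 450 | 10.0 / 10.3 / 9.8 | 9.6 / 10.3 / 9.8 | 7.2 / 32.5 / 71.3 | 0.1 / 0.7 / 3.0 |
| 480 | 0.00 / 0.01 / 0.00 | 0.00 / 0.01 / 0.00 | 7.6 / 32.6 / 71.4 | 0 / 0 / 0 |
| 500 | 0 / 0 / 0 | 0 / 0 / 0 | 7.5 / 32.5 / 71.1 | 0 / 0 / 0 |

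At the liberal 450 cut, the mean change among computable pairs is 5.4 msec when the truth is 10, and 11.8 when it is 20.

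**6. Triplicate averaging.** In the same runs, where QTcF alone triggers the CS call, the mean of the CS replicates exceeds the full-triplicate mean by 2.4 msec (460.85 − 458.42; cut 450, shift 20) to 7.8 msec (503.20 − 495.43; cut 500, shift 0).

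**The case against.** The strongest case on the other side is that this is one item within a secondary endpoint of a descriptive, single-arm trial whose primary endpoint is the incidence of adverse events. Investigators review ECGs against predose tracings (Protocol 8.2.3). CS findings are tabulated by specific abnormality, and abnormal, clinically significant ECGs are also reported as adverse events (SAP 4.9.4). Protocol 4.3 reports no QT prolongation at any dose level in the earlier 110-participant study. All of this stands. A reader might infer that the trial would miss clinically important QT events altogether; the documents do not support that. These safeguards count judged events, however, and do not deliver the change in intervals that the endpoint names.

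The CS call is an overall judgment, not a QTcF threshold. A reader might infer that every averaged triplicate is biased upward. The documents support that for QTcF only when prolongation prompted the call; an ECG flagged for rhythm or conduction need not have a long QTcF. Likewise, exclusion criterion 5 does not remove every CS ECG finding, so it would go too far to say that nobody has a recorded baseline.

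The recording sentence could be read at participant level rather than tracing level. On either reading, participants with no CS ECG contribute no values, and the summary rule is written for abnormal/CS records.

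A reader might also assume that the central vendor can simply transfer the intervals. Protocol 8.2.3 says only that ECGs are collected and held in case of sponsor questions, and that ECG data for the study report rest on Investigator assessment. Whether numeric intervals are available is not stated.

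**Conclusion.** The point holds. SAP 4.9.4 contradicts the secondary endpoint and Protocol 9.3.3.1, is inconsistent within itself, and is not declared as a departure in SAP 4.13. Followed as written, it makes change from baseline and shifts non-computable for most participants and leaves values selected by the investigator's CS call. That conclusion rests on the recording rule and the eligibility criteria, not on the simulation.

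The simulated counts (0 to about 10 of 100 participants with a computable change) depend wholly on assumed distributions and on treating the CS call as a QTcF cut, so they are not forecasts. Nor does the maximum of 5,600 tracings mean that 5,600 ECGs are thrown away: tracings are reviewed and held, and what is lost is interval capture and analysis. The optional QTcF categories share the data problem, but making them mandatory, or counting only newly exceeded thresholds, is a preference rather than a needed correction.

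**What to change.** 1. Capture RR, PR, QRS, QT, QTcB and QTcF for every protocol ECG. Either open the eCRF fields for all ECGs or, if numeric intervals are available, take them from the centrally held ECGs. The second route must be reconciled with the Investigator-assessment statement in Protocol 8.2.3.
2. Delete the abnormal/CS restriction from SAP 4.9.4.
3. Average all available replicates at each timepoint.
4. Define the ECG baseline consistently with SAP 4.2.1, as the mean of the last pre-treatment set.
5. Summarise values, changes, shifts and CTCAE QTcF grades for all participants with data, by line of therapy and visit/timepoint. Keep the existing table of clinically significant findings alongside.
6. If full capture is not possible, declare the departure in SAP 4.13, label the tables as limited to abnormal/CS records, and do not present them as the ECG change-from-baseline endpoint.

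No new ECGs or readers are needed. The cost is SAP wording plus data entry or data-management work, including back-entry for ECGs already done. The documents do not allow that effort to be sized.
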